#### 5.3.11.2 Timing of Disease Assessment

Tumour imaging may be performed by CT. The initial tumour imaging will be performed no more than 28 days prior to confirmation of eligibility. Scans performed as part of routine clinical management are acceptable for use as the screening scan if they are of diagnostic quality and performed within the correct time window.

On-study imaging will be performed at screening every 3 cycles (every 9 weeks) for the first 6 months ( $\pm$  7 days) then every 12 weeks after 6 months ( $\pm$  7 days), and should follow calendar days and should not be adjusted for delays in cycle starts or extension of pembrolizumab cycle frequencies. Tumour imaging and assessment per local standard of care should be performed for patient management and may include additional imaging (e.g. bone scan). Imaging should continue to be performed until documented disease progression, the start of new anti-cancer treatment, withdrawal of consent, death, or the end of the study, whichever occurs first.

### **5.3.11.3 Confirmation of Disease Response**

Per RECIST v1.1 & irRC (Appendix 6 & 7), response should be confirmed by a repeat radiographic assessment no less than 4 weeks from the date the response was first documented. The scan for confirmation of response may be performed at the earliest 4 weeks after the first indication of response, or at the next scheduled scan, whichever is clinically indicated.

Immunotherapeutic agents may produce anti-tumour effects by potentiating endogenous cancer-specific immune responses. The response patterns seen with such an approach may extend beyond the typical time course of responses seen with cytotoxic agents and can manifest a clinical response after an initial increase in tumour burden or even the appearance of new lesions. Therefore standard RECIST v1.1 may not provide an accurate response assessment of immunotherapeutic agents such as pembrolizumab.

Therefore, RECIST v1.1 will be used with the following adaptations:

- If radiologic imaging shows initial progressive disease (PD), tumour assessment should be repeated  $\geq 4$  weeks later in order to confirm PD with the option of continuing treatment while awaiting radiologic confirmation of progression.
  - Patients may continue treatment while waiting for confirmation of PD if they are clinically stable as defined by the following criteria:
    - Absence of signs and symptoms indicating disease progression
    - No decline in ECOG performance status
    - Absence of rapid progression of disease
    - Absence of progressive tumour at critical anatomical sites requiring urgent alternative medical intervention. When feasible, patients should not be discontinued until progression is confirmed. This allowance to continue treatment despite initial radiologic progression takes into account the observation that some patients can have a transient tumour flare in the first few months after the start of immunotherapy, but with subsequent disease response. Patients that are deemed clinically unstable are not required to have repeat imaging for confirmation of progressive disease.

- If repeat imaging shows a reduction in the tumour burden compared to the initial scan demonstrating PD, treatment may be continued /resumed.
- If repeat imaging confirms progressive disease, patients will be discontinued from study therapy.
  - NOTE: If a patient with confirmed radiographic progression (i.e. 2 scans at least 28 days apart demonstrating progressive disease) is clinically stable or clinically improved, and there is no further increase in the tumour dimensions at the confirmatory scan, an exception may be considered to continue treatment upon consultation with the Sponsor. Clinically stable patients should also have at the confirmatory scan no further increase in the target lesions, no unequivocal increase in non-target lesions, and no additional new lesions develop (non-worsening PD) to continue study treatment.

In determining whether or not the tumour burden has increased or decreased, investigators should consider all target lesions as well as non-target lesions.

#### **5.3.11.4 Confirmation of Disease Progression**

Disease progression should be confirmed at least 4 weeks after the first scan indicating progressive disease in clinically stable patients. Patients who have unconfirmed disease progression may continue on treatment until progression is confirmed.

Clinically stable is defined by one or more of the following criteria:

- Absence of signs and symptoms indicating disease progression
- No decline in ECOG performance status
- Absence of rapid progression of disease
- Absence of progressive tumour at critical anatomical sites (e.g., cord compression) requiring urgent alternative medical intervention

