Directed Phys. Exam			X	X	X	X	X	X	X	X	X					
Adverse Events	X	X	X	X	X	X	X	X	X	X	X	X	X	X		
MRC dyspnea score	X		X	X	X	X	X	X					X			
Medications	X	X	X	X	X	X	X	X	X	X	X	X	X	X		
ECOG PS	X	X	X	X	X	X	X	X	X	X	X	X	X	X		
Vital Signs & Weight	X	X	X			X	X	X	X	X	X	X	X	X		
Height	X															
Haem & Biochem	X 	X 				X 	X 	X 	X 	X 	X 	X 	X	X		
FT3, FT4 and TSH	X 	X					X		X		X		X	X	X	
PT and aPTT	X 															
Pregnancy Test	X 															
Urinalysis	X 															
Pembrolizumab		X				X	X	X	X	X	X	X				
Radiotherapy			X 	X 	X 											
Pulmonary function 	X											X				
Imaging	CT  & CXR 					CXR	CXR	CXR	CT	CXR		CT		CT	CT	
PD-L1 assessment 	X															
Research Blood		X				X			X				X			
Survival Status															X	

1. Imaging with a CT scan should occur during the screening period as a baseline and then every 9 weeks (3 cycles) for the first 6 months, then every 12 weeks after 6 months (regardless of treatment delays). Imaging with CT scanning can occur 7 days before the visit to ensure that the results are available at the visit.
2. Chest x-ray will be performed during the dose limiting toxicity period in order to monitor for pneumonitis.
3. Full pulmonary function tests should be performed every 6 months from radiotherapy.
4. Dose escalation and expansion cohort will not be enriched for PD-L1 strong patients. PD-L1 testing will be batched and performed once all patients are on study.
5. Lung SBRT will be administered at dose level being tested on C1D15, C1D17 and C1D19 during the dose escalation phase, and at the RP2D for C1D15, C1D17 and C1D19 during the dose expansion phase.
6. Screening laboratory investigations will be valid for 10 days from C1D1.
7. Safety laboratory investigations will be valid for 3 days from D1 visit.

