Patients who in the assessment by the investigator, require the use of any of the aforementioned for their clinical management should be removed from the trial. Patients may receive other medications that the investigator deems to be medically necessary. The Exclusion Criteria describes other medications which are prohibited in this trial. There are no prohibited therapies during the Post-Treatment Follow-up Phase.

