#### 8.1.2 Secondary Endpoints

Acute and late toxicity data will be tabulated by type, grade and dose level with the number, proportions and frequencies of grades 1-4 and grade 3-4 grades reported. The duration of clinical benefit assessed by overall response rate (ORR) defined as complete response (CR) or partial response (PR) and disease control rate (DCR) defined as CR, PR or stable disease (SD) using RECIST v1.1 & irRC (Appendix 6 & 7) will be calculated as a proportion of total treated with a 95% confidence interval. Differential response rates, defined as mixed responses , where some sites of disease shows a response to treatment, while other sites of disease show disease progression, will be measured as (yes/no). This will be calculated as proportions in the squamous cell and non-squamous cell histological sub-type giving associated 95% confidence intervals. Any differences will be assessed using a Chi squared test for proportions on differential response rates between histological subtypes. **PD-L1 staining is referred to as tumour proportionate score, reported as a percentage**

from 0–100%. It is classed as weakly positive (1 – 49%); strongly positive if >50%; and negative if <1%. The effect of PD-L1 expression on response rates will be measured using the proportion of patients recorded to be weakly positive, strongly positive or negative and tested using a Chi Squared test for proportions on expression level between responders and non-responders. PFS will be measured from the start of radiotherapy until radiological or clinical evidence of progression or death and will be censored at date of last follow-up for surviving patients. OS will be measured from the start of radiotherapy until death and will be censored at date of last follow-up for surviving patients. Median PFS and OS will be calculated using Kaplan-Meier methods giving associated 95% confidence intervals, respectively. All patients from Part A and Part B will be used to analyse secondary endpoints.

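### Section 5.3.11.4 lets any one of four criteria make a progressing patient clinically stable, in conflict with the unqualified list in Section 5.3.11.3

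*Combined protocol and SAP*

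**What the plan says.** Two neighbouring sections of the combined protocol and SAP deal with a patient whose scan first shows progressive disease (PD).

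Section 5.3.11.4 (Confirmation of Disease Progression) opens with who needs a second scan: "Disease progression should be confirmed at least 4 weeks after the first scan indicating progressive disease in clinically stable patients". It goes on: "Patients who have unconfirmed disease progression may continue on treatment until progression is confirmed". It then defines the term: "Clinically stable is defined by one or more of the following criteria". Four criteria follow. In short: no signs or symptoms of progression; ECOG status no worse; disease not progressing rapidly; and no progressing tumour at a critical site that needs other treatment urgently. Cord compression is given as the example for the fourth.

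Section 5.3.11.3 (Confirmation of Disease Response) contains the rule on dosing: "Patients may continue treatment while waiting for confirmation of PD if they are clinically stable as defined by the following criteria". The same four criteria follow, without the cord compression example and without any word saying whether one or all must hold. The same section says that unstable patients need no repeat imaging. It also allows an exception after confirmed PD, in consultation with the sponsor, for a patient who "is clinically stable or clinically improved, and there is no further increase in the tumour dimensions at the confirmatory scan".

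Section 6.8.1 lists confirmed radiographic progression as a reason to stop trial medication and refers the reader to Section 6.3.11.4, which does not exist. A note there lets a patient with confirmed progression be granted an exception if stable or improved.

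**The concern.** The four criteria are safety conditions. Each describes a way in which waiting at least four weeks on the same treatment could be wrong for the patient. A rule under which any one of them is enough lets the most serious warning be outweighed by the mildest reassurance: progressing tumour that needs urgent treatment is cancelled by an unchanged performance status.

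Two investigators who read neighbouring sections could therefore classify the same patient differently. The classification decides who is directed to a confirmatory scan. Through Section 5.3.11.3, it also decides who may stay on pembrolizumab while waiting. A lesser point lies in the same place: the 5.3.11.4 sentence on continuing treatment does not repeat the stability condition.

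**Working it through.** The plan gives no figure on this point, so there is none to reproduce. The check is a comparison of the two texts and a count of what each rule implies.

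**Step 1: the texts side by side.**

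| | Section 5.3.11.3 | Section 5.3.11.4 |
|---|---|---|
| Criteria | Four | The same four, with cord compression as an example in the fourth |
| How many must hold | Not stated | One or more |
| What stability governs directly | Continuing treatment before PD is confirmed | Who should have PD confirmed by a later scan |
| Stability condition in the sentence on continuing | Yes | Not repeated |

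**Step 2: what the unqualified list means.** Section 5.3.11.3 does not say *all*. A definition followed by a plain list of conditions is naturally read as requiring each of them. The content supports this, since a need for urgent alternative treatment cannot sensibly be offset by an unchanged ECOG status. The all-four reading is still an inference. If both sections were read as needing only one criterion, the conflict would go but the unsafe result would then apply in both.

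**Step 3: how far apart the rules are.** Each criterion is met or not met.

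- Patterns: 2^4 = 16.
- Stable if at least one is met: 16 − 1 = 15.
- Stable if all four are met: 1.
- Patterns classified differently: 15 − 1 = 14.

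Now fix the critical-site criterion as failed, so that three criteria remain free.

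- Patterns: 2^3 = 8.
- Stable under the one-or-more rule: 8 − 1 = 7.
- Stable under the all-four rule: 0.

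One of those 7 is a patient with cord compression, symptoms and rapid progression whose ECOG status has not changed. Section 5.3.11.4 calls that patient stable.

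**Step 4: which section a reader would use.** The number in 6.8.1 is wrong, but its ending and its subject match 5.3.11.4. An investigator who follows it arrives at the one-or-more definition. The note in 6.8.1 then uses the idea of clinical stability without repeating the non-worsening scan or the sponsor consultation that 5.3.11.3 requires.

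**Step 5: the sentence on continuing.** It stands between a sentence limited to stable patients and the definition of that term. Context suggests that the condition carries over, but the sentence does not state it.

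**The case against.** The strongest reply is that Section 5.3.11.3 governs dosing and carries its own list. In 5.3.11.4 the term directly decides only who has progression confirmed, so the sections clash over treatment only if someone takes the definition from one into the other. That is right about direct use. It does not remove the conflict: one term has two definitions in adjacent sections, and 6.8.1 leads the reader to the looser one.

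Second, 5.3.11.3 never says *all*. This stands as a limit on the claim, as Step 2 sets out.

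Third, the missing condition in the sentence on continuing treatment is supplied by its neighbours and by 5.3.11.3. This largely stands, and the point is minor.

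Fourth, the pattern counts weight every pattern equally although the criteria are clinically linked. This also stands. The counts show how far apart the rules are, not how often they would diverge in practice.

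Fifth, other provisions protect patients:

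- Continuing is optional in both sections.
- The exception after confirmed PD in 5.3.11.3 needs a non-worsening scan and sponsor consultation.
- Section 5.1 requires treatment beyond progression to be discussed with the sponsor and the drug's manufacturer.
- Under 6.3.1, patients who "require the use of any of the aforementioned for their clinical management should be removed from the trial", subject to a limited radiotherapy exception agreed with the chief investigator.
- Sections 6.8.1 and 6.9 let treatment be stopped.

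These limit the harm but leave the wrong definition in place.

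A reader might be tempted to go further in three ways, none supported by the documents.

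- *PFS is biased, or is safe from bias.* Section 8.1.2 says "PFS will be measured from the start of radiotherapy until radiological or clinical evidence of progression or death" but not whether the first or the confirming scan dates the event. Neither harm nor reassurance follows.
- *Dose finding is affected.* DLTs are defined by toxicity in 3.2.1, and no effect on DLT assessment, MTD or RP2D is claimed.
- *A definite number of excess doses would be given.* Section 6.2.7 lets each dose move by up to 3 days either way, no maximum wait for confirmation is stated, and continuing is optional. No exact count can be defended.

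**Conclusion.** The point holds. The definition in 5.3.11.4 is a stated rule that gives a wrong result, and it conflicts with the natural reading of 5.3.11.3. The two readings disagree on 14 of 16 logical patterns. With the critical-site criterion failed, 7 of 8 patterns still count as stable under 5.3.11.4.

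The conflict rests on one assumption: that the unqualified list means all four. The fault in 5.3.11.4 taken alone does not depend on it. The number of patients affected cannot be estimated from the documents. It would be too much to conclude that patients with cord compression will in fact be kept on pembrolizumab, because the safeguards make that unlikely to pass unchallenged. This is a correction that should be made, not a fault that undermines the trial's main results.

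**What to change.** 1. In 5.3.11.4, replace *one or more of the following criteria* with *all of the following criteria*.
2. In 5.3.11.3, insert *all of* before *the following criteria* in the definition of clinically stable.
3. In 5.3.11.4, begin the sentence on continuing treatment with *Clinically stable patients who have*, leaving the rest as it is.
4. As an editorial correction, change *Section 6.3.11.4* in 6.8.1 to *Section 5.3.11.4*.

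The cost is three short wording changes and one cross-reference, with no change to the design or the sample size. There is a small downside: fewer patients will count as stable, so fewer will be directed to a confirmatory scan. Section 5.3.11.3 only says that unstable patients do not need one, so a repeat scan remains possible where the investigator wants it.

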### **5.3.12 Tumour Tissue Collection and Correlative Studies Blood Sampling**

#### **5.3.12.1 Archival Tumour tissue samples**

For patients where a screening biopsy is not feasible, archival tumour material must be provided. If archived biopsy (block or slides) are sent it must contain tumour tissue. If no block is available, 10 or more freshly prepared (generated within the last 6 months) unstained 5 micron sections should be provided. Archival tumour blocks will be returned to source at the end of the study or, upon request, earlier if required for the patient's clinical management. Cut sections will be retained by the study team. These are archived samples and as such participating patients will not need to attend extra visits or undergo extra procedures. All collected archival samples will be classed as pre-treatment samples and used as such in the immunological evaluation as described below.

### 5.3.13 Tumour Biopsies and Research Blood Samples

For patients without archived samples, tumour biopsies will be obtained during the screening period. If the patient consents optional research blood samples will be obtained at C1D1, C2D1, C5D1 and at the end of study visit (Table 3). Tumour and blood samples from this study may undergo proteomic, genomic and transcriptional analyses. Additional research may evaluate factors important for predicting responsiveness or resistance to pembrolizumab therapy and radiotherapy. Assays may include, but are not limited to:

- **Characterization of TILs and tumour antigens**

Immunohistochemistry (IHC) will be used to assess the number and composition of immune infiltrates in order to define the immune cell subsets present within formalin-fixed, paraffin embedded (FFPE) tumour tissue before and after exposure to therapy. These IHC analyses will include, but not necessarily be limited to, the following: CD4, CD8, FOXP3, PD-1, PD-L1, and PD-L2.

- **ctDNA & CTCs**

Research blood samples will be analysed for ctDNA and CTCs. Analysis of CTCs will include, but not necessarily limited to the following, the diagnostic performance of PD-L1 testing will be assessed in CTC compared with IHC, correlation with response and disease progression.

### 5.3.14 Chain of Custody of Biological Samples

In all cases, patients will be consented for the collection and use of their biological samples and a full chain of custody will be maintained for all samples throughout their lifecycle. The Investigator is responsible for maintaining a record of full traceability of biological samples collected from patients while these are in storage at the site, either until shipment or disposal. Anyone with custody of the samples e.g. sub-contracted service provider will have to keep full traceability of samples from receipt to further shipment or disposal (as appropriate). RM-CTU will keep overall oversight of the entire lifecycle through internal procedures and monitoring of study site.

## 5.4 Total Blood Volume

The total volume of blood that will be drawn from each trial patient for the assessments described in the sections above is shown in Table 5.

**Table 5:** Volume of blood

	Sample volume (ml)	No. of samples	Total volume (ml)
Routine Haematology	6 	11	66
Routine Chemistry	8 	11	88
Routine Total:			154
Research Blood Samples OPTIONAL	Up to 60	4	240
Study Total:			394

 Blood volumes may vary according to local practice

## 6 TREATMENTS

---

### 6.1 Lung SBRT

#### 6.1.1 Planning and Delivery

Radiotherapy planning and delivery should be carried out in accordance with the current RTT QA guidelines for stereotactic radiotherapy trials available on request from RM-CTU and included as Appendix 3 within the protocol. As only part of a lung lesion may be treated the target coverage planning goals will be for the defined target volumes.

#### 6.1.2 Toxicity Assessments

Dyspnoea score and toxicity grading with CTCAE v4.0 will be recorded and will include pneumonitis, lung fibrosis, oesophagitis, skin toxicity, myelitis and fatigue. Side-effects that are seen with lung stereotactic radiotherapy include pericarditis, dysphagia, gastrointestinal bleeding, gastrointestinal ulceration, esophagitis, gastritis, nausea, vomiting, cough, pneumonitis, dyspnoea, fatigue, skin erythema, chest wall pain, and rib fracture. All other AEs will be documented in addition.

### 6.2 Pembrolizumab

#### 6.2.1 Investigational Product

The Investigational Medicinal Product (IMP) for this study is pembrolizumab. A potent and highly-selective humanized mAb of the IgG4/kappa isotype designed to directly block the interaction between PD-1 and its ligands, PD-L1 and PD-L2. Pembrolizumab potentiates existing immune responses only in the presence of antigen and does not non-specifically activate T-cells. Pembrolizumab will be manufactured by MSD according to Good Manufacturing Practice and will be provided in the formulation as described in Table 6. Additional information about the investigational product can be found in the Summary of Product Characteristics (SmPC).

**Table 6:** Product Description

Product Name & Potency	Formulation
Pembrolizumab 100 mg/ 4mL	Solution for Injection

#### 6.2.2 Product Preparation

Please refer to the RM CTU Pharmacy Manual for preparation of the pembrolizumab for infusion.

## 6.2.3 Storage and Handling

### 6.2.3.1 Storage

The original solution for infusion should be stored at refrigerated conditions (2 – 8 °C). Vials should be stored in the original box to ensure the drug is protected from light.

Prepared infusion solutions may be stored at room temperature for a cumulative time of up to 4 hours. This includes room temperature storage of reconstituted drug product solution in vials, room temperature storage of admixture solutions in the IV bags and the duration of infusion. In addition, reconstituted vials and/or IV bags may be stored under refrigeration at 2 °C to 8 °C (36 °F to 46 °F) for up to 20 hours. If refrigerated, allow the vials and/or IV bags to come to room temperature prior to use.

